
the outcome of the study. These include, but are not limited to, a PR interval >200 msec, a corrected QT interval [QTc] >450 msec for male subjects and >470 msec for female subjects, or any evidence of heart block, right bundle branch block, or left bundle branch block.
 
d. History or presence of any clinical condition or evidence of organ dysfunction that may affect either the subject's ability to participate in the study or the study result, in the opinion of the Investigator.e. Subjects with abnormal liver function values. These will include aspartate transaminase (AST), alanine transaminase (ALT) or alkaline phosphatase (ALP) $\geq 3 \times$ ULN at screening.f. Subject with abnormal renal function values (serum creatinine $\geq 1.7 \times$ ULN with creatinine clearance level ≤ 75 mL/min at screening).g. In the opinion of the Investigator, the subject has active tuberculosis.h. Uncontrolled diabetes mellitus (defined as known by the case of HbA1c >8%).i. Uncontrolled hypertension (defined as known by the case of systolic blood pressure (SBP) ≥ 160 mmHg or diastolic blood pressure (DBP) ≥ 100 mmHg).j. Documented, known current infection with hepatitis B, hepatitis C, or human immunodeficiency virus (HIV).k. Severe infection within 30 days prior to the administration of study drug that required parenteral antibiotic use or hospitalization.l. Any uncontrolled acute or chronic clinically significant respiratory disease (e.g., chronic obstructive pulmonary disease, cystic fibrosis, bronchiectasis, asthma, or bacterial pneumonia).m. History of malignancy within 2 years prior to study drug administration (with the exception of treated basal cell carcinoma of the skin or carcinoma in situ of the cervix) or current active malignancy. 
8. Subject is currently hospitalized or currently requires hospitalization due to severity of illness or has any plan for elective hospitalization within 1 month after study drug administration.9. Subject requires oxygen therapy due to underlying disease or influenza infection.10. Subject has a history of bone marrow or solid organ transplantation.11. Subject uses systemic steroids or other immunosuppressant (except oral steroid up to 5-10 mg/day, methotrexate up to 10 mg/week).12. Subject requires routine/intermittent hemodialysis or peritoneal dialysis.13. Subject is pregnant or breastfeeding.14. Subject is not eligible for the study participation for whatever reason (including clinical laboratory results) in the opinion of the Investigator, or shows evidence of a condition (psychological, emotional problems, any disorders or resultant therapy) that is likely to invalidate informed consent, or limited the ability of the subject to comply with the protocol requirements in the opinion of the Investigator, or unable to understand the protocol requirements, instructions and study related restrictions, the nature, scope and possible consequences of the clinical study, or is unable to give written informed consent or to comply fully with the protocol.

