ADE=antibody-dependent enhancement; AE=adverse event; ECG=electrocardiogram; eCRF=electronic case report form; EOS=End of Study; Flu -iiQ™=Influenza Intensity and Impact Questionnaire; HI=hemagglutination inhibition; HIV=Human immunodeficiency virus; PK=pharmacokinetic

Note: The assessments designated with an (X) will only be performed in selected subjects under the conditions explained in the footnotes.

1. For most subjects, obtainment of the informed consent form (ICF), screening for eligibility, randomization and treatment will occur on the same day. Though obtainment of the ICF may occur on the day prior to screening, randomization or treatment, it must be within 24 hours before the administration of study drug.
2. Hepatitis B surface antigen, Hepatitis B surface antibody, Hepatitis C virus antibody, and HIV will be assessed at screening in all subjects (mandatory). The results of these tests are not intended as eligibility assessments, but collected to provide baseline information.
3. For females of child-bearing potential only.
4. Urine pregnancy test will be performed at screening. If the urine pregnancy test gives equivocal results, a serum pregnancy test will be performed prior to study drug administration. Subjects with a positive test result will be excluded from the study.
5. Clinical laboratory analysis will be performed at screening and on Day 3, Day 8. All clinical laboratory analysis will be performed at the local laboratory. The laboratory tests to be performed are presented in [Table 3](#).
6. Clinical laboratory results will not be used for assessment of eligibility, but to establish baseline values.
7. Vital sign will be performed at screening, Day 1 (prior to infusion), Day 2 (±4 hours), Day 3 (±4 hours), Day 5 (±4 hours), Day 8 (±4 hours) and Day 110 (±5 days) after the start of the study drug infusion. Blood pressure (sitting) and heart rate will be measured after the subject has rested (sitting quietly) for at least 5 minutes.
8. 12-Lead ECGs will be performed at screening, on Day 8 (±4 hours), and Day 110 (±5 days) (or EOS visit in early termination case).
9. Chest x-rays to evaluate the lower respiratory tract will be performed at screening and if the Investigator considers it is clinically appropriate, chest x-rays to evaluate the lower respiratory tract will be performed during the study.

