4.3.2 Exclusion Criteria

Subjects who meet any of the following criteria will be excluded from the study:

1. Subject is not likely to complete all required study visits or procedures for any reason, in the opinion of the Investigator.
2. Subject has received a treatment with another investigational medical product or participated in another clinical trial within 30 days (or 5 half-lives, whichever is longer).
3. Subject has previous exposure to any anti-influenza monoclonal antibody therapy including CT-P27 prior to study drug administration.
4. Subject has a history of hypersensitivity to any monoclonal antibody or has a known hypersensitivity to any of the treatment components.
5. Subject is taking antiviral treatment for influenza (e.g., zanamivir, oseltamivir, rimantadine, amantadine, peramivir, or ribavirin) or has a history of using these antivirals within 14 days prior to the administration of study drug.
6. Subject has been immunized against influenza with live attenuated or inactivated virus vaccine within 21 days prior to the administration of study drug.
7. Subject has a medical condition including one or more of the following:
 - a) Positive influenza B or influenza A+B infection.
 - b) History or presence of congestive heart failure with symptoms consistent with New York Heart Association Class III or IV functional status within 12 months prior to study drug administration.
 - c) Presence of clinically significant abnormality on a 12-lead ECG at screening that, in the Investigator's clinical judgment, may compromise the safety of the subject or affect the outcome of the study. These include, but are not limited to, a PR interval >200 msec, a corrected QT interval [QTc] >450 msec for male subjects and >470 msec for female subjects, or any evidence of heart block, right bundle branch block, or left bundle branch block.
 - d) History or presence of any clinical condition or evidence of organ dysfunction that may affect either the subject's ability to participate in the study or the study result, in the opinion of the Investigator.
 - e) Subjects with abnormal liver function values. These will which include aspartate transaminase (AST), alanine transaminase (ALT) or alkaline phosphatase (ALP) $\geq 3 \times$ ULN at screening.
 - f) Subject with abnormal renal function values (serum creatinine $\geq 1.7 \times$ ULN with creatinine clearance level ≤ 75 mL/min at screening).

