 - g) In the opinion of the Investigator, the subject has active tuberculosis.

- h) Uncontrolled diabetes mellitus (defined as known by the case of HbA1c >8%).
 - i) Uncontrolled hypertension (defined as known by the case of systolic blood pressure (SBP) \geq 160 mmHg or diastolic blood pressure (DBP) \geq 100 mmHg).
 - j) Documented, known current infection with hepatitis B, hepatitis C, or human immunodeficiency virus (HIV).
 - k) Severe infection within 30 days prior to the administration of study drug that required parenteral antibiotic use or hospitalization.
 - l) Any uncontrolled acute or chronic clinically significant respiratory disease (e.g., chronic obstructive pulmonary disease, cystic fibrosis, bronchiectasis, asthma, or bacterial pneumonia).
 - m) History of malignancy within 2 years prior to study drug administration (with the exception of treated basal cell carcinoma of the skin or carcinoma in situ of the cervix) or current active malignancy.
8. Subject is currently hospitalized or currently requires hospitalization due to severity of illness, or has any plan for elective hospitalization within 1 month after study drug administration.
9. Subject requires oxygen therapy due to underlying disease or influenza infection.
10. Subject has a history of bone marrow or solid organ transplantation.
11. Subject uses systemic steroids or other immunosuppressant (except oral steroid up to 5-10 mg/day, methotrexate up to 10 mg/week).
12. Subject requires routine/intermittent hemodialysis or peritoneal dialysis.
13. Subject is pregnant or breastfeeding.
14. Subject is not eligible for the study participation for whatever reason (including clinical laboratory results) in the opinion of the Investigator, or shows evidence of a condition (psychological, emotional problems, any disorders or resultant therapy) that is likely to invalidate informed consent, or limited the ability of the subject to comply with the protocol requirements in the opinion of the Investigator, or unable to understand the protocol requirements, instructions and study related restrictions, the nature, scope and possible consequences of the clinical study, or is unable to give written informed consent or to comply fully with the protocol.

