5.5 Method of Assigning Subjects to Treatment Group

Once the subject has provided an informed consent and meets all the inclusion criteria and none of the exclusion criteria, the study site will request the study drug assignment using the Interactive Web Response System (IWRS).

All randomized subjects will be managed by IWRS. To randomize a subject, the study site will access the IWRS interlocking with electronic data capture system. The subject identifying information (e.g. gender, year of birth and/or date of birth) and the stratification factors are provided to gain the randomization number and investigational product allocation. Randomization information which includes randomization ID, regime name, regime ratio, date and time of randomization, and stratum name generated by IWRS will be delivered to the Sponsor.

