
Hematology: White blood cell count (WBC) with differential, including absolute neutrophil count Red blood cell (RBC) count Hematocrit (HCT) Hemoglobin (Hb) Platelet count
 
Urinalysis: Color pH Specific gravity Ketones Protein Glucose Bilirubin Nitrite Urobilinogen Occult blood Microscopic examination of sediment
 
Additional Tests (Screening only): Hepatitis B surface antigen Hepatitis B surface antibody Hepatitis C virus antibody Human immunodeficiency virus (HIV)
	
Serum Chemistry: Albumin Alkaline phosphatase Alanine aminotransferase (ALT) Aspartate aminotransferase (AST) Blood urea nitrogen (BUN) Chloride Creatine kinase (CK) CK enzyme subtype* Troponin* Serum creatinine Creatinine clearance (estimated by weight and by Cockcroft-Gault formula) C-reactive protein Cholesterol Glucose Lactate dehydrogenase (LDH) Potassium Sodium Total bilirubin Direct bilirubin Total protein Uric acid Triglyceride
 
Additional Tests (Screening and Day 110/EOS visit): Urine pregnancy (women of childbearing capacity) Serum pregnancy test Note: Urine pregnancy test will be performed before study drug administration in females of childbearing potential only. If the urine pregnancy test gives equivocal results, a serum pregnancy test will be performed to determine if the subject is pregnant. Pregnant women will be excluded from this study at screening.
 
*Relevant assessment for CK enzyme subtype and Troponin will be performed only when CK result shows a clinical significance.

--	--

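### Table 1 footnote 6 says screening laboratory results do not decide eligibility, contradicting exclusions 7e and 7f and the Section 5.5 randomization condition

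*Protocol*

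**What the plan says.** Footnote 6 belongs to the screening cell of the clinical laboratory row in Protocol Table 1 (Section 4.1). It reads: "Clinical laboratory results will not be used for assessment of eligibility, but to establish baseline values". The SAP's schedule (14.1) carries the same footnote. Footnote 5 identifies the row as the Table 3 panel, run at the local laboratory at screening, Day 3 and Day 8.

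Protocol 4.3.2 uses results from that panel as entry limits:

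- Exclusion 7e covers "Subjects with abnormal liver function values", with the limit at AST, ALT or ALP of 3 × ULN or more at screening.
- Exclusion 7f begins "Subject with abnormal renal function values (serum creatinine" and requires a value of 1.7 × ULN or more together with creatinine clearance of 75 mL/min or less at screening.
- Exclusion 14 is a matter of judgement: "Subject is not eligible for the study participation for whatever reason (including clinical laboratory results) in the opinion of the Investigator".
- Exclusion 7d, also a matter of judgement, covers evidence of organ dysfunction that may affect participation or the study result.

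The synopsis repeats these exclusions. Section 5.5 applies them at randomization: once a consented subject "meets all the inclusion criteria and none of the exclusion criteria, the study site will request the study drug assignment".

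**The concern.** The same blood sample is irrelevant to entry under the footnote and can disqualify under 7e or 7f. One site could randomize before its local results return because the schedule says they do not matter. Another could wait because 4.3.2 and 5.5 say they do. The subjects at issue have marked liver or kidney abnormality, and the protocol means to keep them from receiving an investigational antibody infusion.

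There is also a consequence for the record. A subject entered in line with the footnote may later be found to have breached an exclusion criterion, which Protocol 11.2.2 treats as a deviation to be graded. The site would then be cited for following the protocol's own schedule.

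**Working it through.** No figure in the plan bears on this point, so the check is a comparison of the texts.

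1. **Does the footnote cover the analytes in 7e and 7f?** Yes. Through footnote 5 the row is the Table 3 panel. Its chemistry list includes "Alkaline phosphatase Alanine aminotransferase (ALT) Aspartate aminotransferase (AST"), and also serum creatinine and creatinine clearance. All five analytes are therefore in the draw that the footnote sets aside.

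2. **Do 7e and 7f rest on that draw?** Yes. Both are tied to values at screening, not to history. Compare exclusion 7j: "Documented, known current infection with hepatitis B, hepatitis C, or human immunodeficiency virus (HIV"). Its wording looks to infection that is already known, which sits more easily with footnote 2, where screening serology is likewise declared not to decide eligibility. Exclusions 7e and 7f carry no such limit.

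3. **Can the footnote be read as loose wording?** Not easily. Table 1 separates tests that decide entry from those that do not. Footnote 4 excludes subjects with a positive pregnancy test. Footnote 8 (ECG, used in exclusion 7c) has no disclaimer. Footnotes 2 and 6 expressly say that the results are not for eligibility.

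4. **Does timing matter?** Yes. Section 5.5 requires that no exclusion is met before assignment is requested, so 7e and 7f can be applied only if the results are in hand. Footnote 1 says that most subjects are screened, randomized and treated on one day, so a site following footnote 6 has no reason to wait.

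5. **Where do the rules give opposite answers?**

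| Screening result | Footnote 6 | 4.3.2 with 5.5 |
|---|---|---|
| AST, ALT or ALP ≥ 3 × ULN | not considered | excluded (7e) |
| Creatinine ≥ 1.7 × ULN and clearance ≤ 75 mL/min | not considered | excluded (7f) |
| Creatinine ≥ 1.7 × ULN, clearance > 75 mL/min | not considered | not excluded by 7f; Investigator judgement (7d, 14) |
| Other abnormal result | not considered | Investigator judgement (7d, 14) |

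The first two rows are outright contradictions. In the last two the footnote sits awkwardly with the protocol, because 7d and 14 may draw on laboratory results.

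6. **Is there a tie-breaker?** None was found in the Protocol or the SAP.

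**The case against.** The strongest reply is that the text as a whole favours the exclusions. The synopsis, 4.3.2 and 5.5 agree, and Table 1 has its own inclusion/exclusion row at screening, so a careful site would apply 7e and 7f whatever the footnote says. That has force. Inconsistent practice across sites is an inference, not something the documents show. But the reply indicates which rule should win; it does not remove the instruction attached to the laboratory cell.

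Protocol 4.1 also lets results already obtained within the screening period serve as screening data. This eases the timing but not the conflict, since those results would still be laboratory results used for eligibility.

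Three stronger readings are tempting, and the documents do not support them:

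- *Exclusion 14 is breached in the same way as 7e and 7f.* It applies only if the Investigator judges the subject ineligible. A site that forms no such opinion has not breached it. The same holds for 7d.
- *Any such entry leads to withdrawal, without replacement under 4.3.4.* Section 11.2.2 makes a deviation significant only when it results in significant additional risk to the subject. It says that entry-criterion breaches can be among these, and has deviations graded minor or major in agreement with the sponsor. Withdrawal is possible, not automatic.
- *The primary analysis is compromised.* The ITTI population is defined by randomization and virological confirmation, which this conflict does not alter.

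Finally, SAP 1.1 describes recruitment over two influenza seasons in the past tense. If enrolment is complete, rewording the footnote changes no one's entry. That objection stands, and it changes the remedy.

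**Conclusion.** The contradiction between footnote 6 and exclusions 7e and 7f is direct and is in the current text. As written, the footnote is a wrong operative rule: a site following it could dose a subject whom the protocol excludes on hepatic or renal grounds. The conflict with 7d and 14 is weaker, for the reason given above.

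The consequences concern subject safety, uniform entry and the grading of deviations. No effect on the estimate, alpha or power is claimed. The number of subjects affected cannot be derived, because the documents give no frequency of screening values beyond the 7e or 7f limits.

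The conclusion about which rule should govern assumes that the sponsor intended the exclusions to apply. The synopsis, 4.3.2 and 5.5 all point that way.

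**What to change.** Replace footnote 6 in Protocol Table 1 with:

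> Screening AST, ALT, ALP, serum creatinine and creatinine clearance are used to assess exclusions 7e and 7f and must be available before randomization; other clinical laboratory results establish baseline values, subject to Investigator judgement under exclusions 7d and 14.

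Align the copy in SAP 14.1, which has no operational effect. No new assay is needed, because all five analytes are already in the local screening panel.

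The cost is a protocol amendment, with IRB/IEC approval before subjects are enrolled under it (Protocol 11.2.1), and a wait for local results inside the 48-hour window (60 hours at most). Laboratory turnaround is not stated, so some subjects could be delayed or miss the window. The new wording only makes explicit a wait that 5.5 and the screening basis of 7e and 7f already imply.

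Limiting 7e and 7f to documented, known values on the model of 7j is not recommended. A screening result returned before randomization is itself documented and known, so the ambiguity would remain.

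If enrolment is already complete, record before unblinding that 7e and 7f are the governing rule, and apply them when entry deviations are classified at the blinded data review (SAP Section 6). The inclusion/exclusion deviation type already exists there. The same decision helps settle who counts as a screening failure randomized by accident, whom SAP 5.3 removes from the ITT population if undosed.

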4.2 Discussion of Study Design

This study uses a standard randomized, placebo-controlled study design. The study is designed to determine the effect size of two doses of CT-P27.

The selection of the study Cohort is appropriate for the evaluation of CT-P27 in subjects with acute, uncomplicated influenza A.

Placebo-controlled trials are appropriate in settings and Cohorts where the expected serious risk of non-treatment is small. For trials evaluating treatment of uncomplicated mild to moderate influenza, placebo-controlled rather than non-inferiority designs will be used because the risks associated with receiving placebo are low, and the efficacy of available treatment is modest (1 day difference in time to symptom improvement), variable, and cannot be predicted well enough to support an adequate non-inferiority margin. The variable clinical course of influenza in any given season, as well as the potential for differences in pathogenicity and host immunity as new influenza strains emerge and change over time, also makes uncontrolled data or historical controls difficult to interpret and inadequate to support efficacy of investigational drugs.

The doses were selected based on PK/PD modelling. The higher dose (90 mg/kg) was evaluated in a Phase I study. No significant adverse effects of treatment were observed.

The primary and secondary efficacy endpoints are consistent with the Food and Drug Administration (FDA) document, “*Guidance for Industry: Influenza: Developing Drugs for Treatment and/or Prophylaxis*”⁶.

4.3 Selection of Study Cohort

Approximately 183 subjects will be enrolled (see [Section 8.1](#)). The study Cohort will consist of male and female subjects with acute uncomplicated influenza A who can be enrolled, screened, randomized, and treated with study drug no more than 48 hours following the onset of symptoms.

4.3.1 Inclusion Criteria

Each subject must meet all the following criteria to participate in this study:

1. Subject is a male or female and aged 19 to 64 years, inclusive.
2. Subject can voluntarily provide a written informed consent.

3. Onset of illness no more than 48 hours prior to the planned administration of study drug. If the adjustments of visit schedule is required, additional 12 hours can be allowed (Maximum onset of illness: 60 hours).

Note: time of onset of illness is defined as the earlier of either (a) the time when the body temperature was first measured as $\geq 38.0^{\circ}\text{C}$ ($\geq 100.4^{\circ}\text{F}$) or (b) the time when the subject experienced the presence of at least two symptoms that are respiratory and/or constitutional (moderate to severe in intensity).

4. As reported by the subject and recorded on the Flu-iiQ™ completed at screening, the subject has at least two of the following symptoms (moderate to severe in intensity):
 - a) Respiratory symptom (cough, sore throat, or nasal congestion) or
 - b) Constitutional symptom (headache, feeling feverish, body aches and pains, or fatigue).
5. Subject has a fever $\geq 38.0^{\circ}\text{C}$ or $\geq 100.4^{\circ}\text{F}$ at screening or a history of fever within the 24 hours prior to screening and has received treatment with an antipyretic(s) in the 6 hours prior to screening.
6. Subject is diagnosed with influenza A at screening, using the Sponsor-supplied or agreed in advance rapid influenza diagnostic test. And if there is available test result confirmed as influenza A prior to obtaining written informed consent and that result was from the influenza diagnostic test which is agreed with Sponsor in advance, that test result can be allowed
7. For both male and female subjects, the subject and his/her partner (if of childbearing potential) agree to use a highly effective method of contraception during the study and for 5 months after the administration of study drug.
 - a) Male and female subjects and their partner who have been surgically sterilized for less than 6 months prior to the date of informed consent must agree to use a highly effective method of contraception during the study and for 5 months after the administration of study drug.
 - b) Menopausal females must have experienced their last menstrual period more than 12 months prior to the date of informed consent to be classified as not of childbearing potential.
8. Subject's body mass index (BMI) is of $< 35.0 \text{ kg/m}^2$ and weight is of $\leq 99.9 \text{ kg}$.

